The obtained result will provide the much needed OSA prevalence in adolescents which is essential for estimating the true burden of disease within this population. This information is also vital when considering population-based health policies and interventional strategies. Globally, the findings from currently evidence-sparse region of the world allow future international comparison of disease burden. Our study will also form a platform from which repeated measurements can be made to assess time trends and to answer the important question of whether adulthood OSA takes its origin from adolescence.

Hypothesis

We hypothesize that the prevalence of obstructive sleep apnoea among adolescents is different from that reported for children.

Key Issues

(1) Our research group has demonstrated that childhood OSA is common in Hong Kong. We found OSA prevalence for boys and girls aged between 5 and 13 years being 5.8% and 3.8% respectively. [1] However, the prevalence of OSA in adolescents remains unknown. It is inaccurate to extrapolate prevalence of childhood OSA to adolescents as they go through a period of critical transition. In fact adolescence is associated with various developmental changes,

namely somatic growth, cerebral remodeling [2] and hormonal changes that can affect upper airway dynamics [3] and ventilator control. [4] These changes are expected to influence upper airway patency during sleep.

The only published study that examined OSA prevalence among adolescents involved a small sample size of 101 subjects. [5] After completion of an 82-item questionnaire, all participants underwent overnight cardiorespiratory monitoring at home. Twenty-nine percent of the subjects were snorers. Polygraphy showed a respiratory disturbance index ≥ 10 in 18 subjects (17.8%), but concurrent symptoms suggestive of OSA were found in only 2 subjects (1.9%). Further studies with sound methodology and a representative sample of the studied population are required to provide a reliable estimation of OSA in adolescents.

(2) Obstructive sleep apnoea in children and adolescents is an important clinically relevant condition because of its association with a number of significant short and long term consequences. [6] Specifically for adolescents, both metabolic disturbances (dyslipidaemia and insulin resistance) and cardiac complications (hypertension, left ventricular diastolic dysfunction and increased left ventricular mass) are well established OSA sequelae. [7-9]

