It is a cross-sectional, population-based study. Subjects who are found to meet all the inclusion and none of the exclusion criteria will be recruited. They will complete a set of sleep-related questionnaires, undergo anthropometric measurements, home polysomnographic (PSG) monitoring, attention assessment and phenotyping of their metabolic and cardiovascular risk.

Pilot Data and Sample Size Estimation

We have previously established a school-based cohort in 2003-2005 which included children aged between 6 and 13 years to determine the prevalence of OSA. [1] We then conducted a 4-year follow-up for a subgroup of the cohort was carried out. [25] At follow-up, the subjects were aged between 10 and 17 years. A total of 243 teenagers returned for the follow-up visit. The prevalence of OSA defined by different cut-offs and the minimum sample size required to detect corresponding prevalence with various levels of precision are presented in table 1. On further analysis those who returned for the 4-year follow-up had higher baseline OSA severity compared to the rest of the cohort [OAHl: 1.0 (0.1–2.5) c.f. 0.6 (0–2.0), $p=0.007$], therefore the calculated prevalence is likely an over-estimation. Nonetheless, using the proposed sample size would provide adequate power should the genuine population prevalence is lower than the calculated one.

Table 1. Minimum sample size required to detect the prevalence of OSA defined by various cut-offs with different levels of precision.

	OAHl $\geq 5/h$	OAHl $\geq 1/h$	OAHl $\geq 1/h$ + habitual snoring (ICSD criteria)
No. of cases	34/243	120/243	31/243
Prevalence	0.140	0.494	0.128
Precision			

	Minimum sample size required		
0.01	4623	9603	4276
0.015	2055	4268	1900
0.02	1156	2401	1069
0.025	740	1536	684
0.03	514	1067	475
0.04	289	600	267
0.05	185	384	171

In the current settings with limited budget allocation, our research team is capable of recruiting 740 adolescents to detect a prevalence of 14.0% with a precision of 2.5% (i.e. 95%CI: 11.5–16.5%) for the OAH1 \geq 5/h cutoff. The sample size can also ensure a precision of <4% for the OAH1 \geq 1/h cut-off and a precision of <2.5% for the ICSD criteria. [31] The sample size would also provide >99% power to detect the differences between the estimated prevalence of OSA in adolescents and the published prevalence of OSA in primary school children [1] no matter which cut-off is being used.

Sampling Frame

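### Does the assurance of adequate power at a lower prevalence, and the unspecified case definition for the comparison with children, undermine the sample size?

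*Combined protocol and SAP*

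**What the plan says.** Pilot Data and Sample Size Estimation takes its prevalences from 243 teenagers followed up from an earlier school cohort: 34 cases by OAHI ≥5/h, 120 by OAHI ≥1/h, and 31 by OAHI ≥1/h with habitual snoring (the ICSD criteria). Those who returned had higher baseline severity than the rest of the cohort, "therefore the calculated prevalence is likely an over-estimation". The protocol then adds that "using the proposed sample size would provide adequate power should the genuine population prevalence is lower than the calculated one". Table 1 follows directly, titled "Minimum sample size required to detect the prevalence of OSA defined by various cut-offs with different levels of precision".

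After the table the target is set at 740 (14.0% ± 2.5 points for OAHI ≥5/h), and a separate claim is made: "The sample size would also provide >99% power to detect the differences between the estimated prevalence of OSA in adolescents" and the published figure for primary school children, "no matter which cut-off is being used".

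The Hypothesis section reads: "We hypothesize that the prevalence of obstructive sleep apnoea among adolescents is different from that reported for children". For children, Key Issues (1) states: "We found OSA prevalence for boys and girls aged between 5 and 13 years being 5.8% and 3.8% respectively". Background of research gives 3–5% by ICSD-II criteria. Outcome Measures defines the adolescent outcome by OAHI without naming a cut-off. Statistical Analysis says only that the result will be compared with the published childhood prevalence, and names neither a test nor a case definition.

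**The concern.** Two things catch the eye.

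First, the section uses the word power, and the only power figure in it belongs to the comparison with children. That figure is worked out at prevalences the protocol has just called too high. A lower adolescent prevalence lies closer to the childhood values, so power falls towards the type I error rate. No lower limit is stated. A reader could not tell at what true prevalence a non-significant comparison stops being informative.

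Second, the only childhood figure tied to a definition is ICSD-II, while the adolescent outcome is defined by OAHI. In Table 1 the same 243 adolescents give 49.4% by OAHI ≥1/h and 12.8% by ICSD criteria. If an OAHI ≥1/h figure were tested against an ICSD-II figure, the difference in definition alone could be reported as support for the study's hypothesis.

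**Working it through.** **Inputs.** From Pilot Data and Sample Size Estimation: n = 740; 34/243 = 0.140, 120/243 = 0.494, 31/243 = 0.128. Child figures: 3.8% and 5.8% (Key Issues), 3–5% (Background). Type I error 0.05 (Statistical Analysis), taken as two-sided because the hypothesis is one of difference. Assumed: 4.8%, the unweighted midpoint of 3.8% and 5.8%; child figure fixed unless stated; design effect D = 1 + 49 × ICC for about 50 pupils per school (Sampling Frame), so ICC 0.02 gives D = 1.98. The documents give no ICC, no child sample size and no size for the over-estimation.

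**1. The plan's own sample size.** n = 1.96² p(1−p)/d². With p = 34/243 and d = 0.025, n = 739.7, so 740 reproduces. The half-width at 740, 1.96 √(p(1−p)/740), is 2.5, 3.6 and 2.4 points for the three definitions, as the protocol says.

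**2. Precision at a lower prevalence.** The same formula (D = 1) gives 2.5 points at 14%, 2.2 at 10%, 1.8 at 7% and 1.7 at 6%. Read as a statement about precision, the assurance is right.

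**3. The stated power.** For child value p0 and adolescent value p1, power = P(p̂ > p0 + 1.96 √(p0(1−p0)D/740)) plus the matching lower tail, under p1. At p1 = 12.8% it exceeds 99.9% for every p0 from 3.0% to 5.8% (D = 1). If the child figure is itself an estimate from an assumed 740 children, power is at least 99.6%. With only 200 children it would be 94% against 4.8%. The claim reproduces for a fixed or reasonably well-estimated child figure.

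**4. Where power runs out.** Example with p0 = 4.8%, p1 = 7%, D = 1: the rejection limit is 0.048 + 0.0154 = 0.0634; the standard error under p1 is 0.0094; (0.0634 − 0.07)/0.0094 = −0.70; power is 76%. At 8% it is 95%, at 6% it is 35%. The lowest true prevalence with 80% power, and its distance below 31/243:

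| Child figure | D = 1 | D = 1.98 |
|---|---|---|
| 3.0% | 4.9% (62% below) | 5.7% (55%) |
| 3.8% | 5.9% (54%) | 6.8% (46%) |
| 4.8% | 7.1% (44%) | 8.2% (36%) |
| 5.8% | 8.3% (35%) | 9.4% (26%) |

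With an assumed 1000 to 6000 children, the D = 1 limit against 4.8% becomes 8.1% to 7.3%. At the pilot's lower 95% Wilson limit of 9.1%, power is 99.6% against 4.8% and 94% against 5.8% (93% and 74% with D = 1.98).

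**5. Mismatched definitions.** Suppose adolescents had exactly the child ICSD prevalence, 4.8%, and the Table 1 ratios held. OAHI ≥1/h would give 0.048 × 120/31 = 18.6%, and a test against 4.8% would reject almost always. OAHI ≥5/h, on which 740 was set, would give 0.048 × 34/31 = 5.3%, with about 10% rejection instead of 5%.

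**The case for a change.** The strongest case for a change is the second part, because it does not depend on how the word power is read. The analysis section governs what is run, and it contains no rule that the two prevalences share a definition. The remark that power holds for any cut-off sits in the sample size section, and no childhood value is given for OAHI ≥1/h or ≥5/h. A literal analyst could produce the 18.6% against 4.8% comparison and report it as support for the hypothesis. The remedy would be a sentence.

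What stands: the definition is not written down, and the childhood values behind the any-cut-off claim cannot be checked from the documents. What does not stand is the step to a wrong result. No part of the protocol proposes testing OAHI ≥1/h against an ICSD figure. The any-cut-off wording is most simply read as a comparison made cut-off by cut-off. The comparator is the investigators' own childhood study, so they know which definitions it reports.

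On the first part, it is fair that the text says power rather than precision, and that stating the prevalence at which power reaches 80% is good practice. But the sentence refers back to the Table 1 prevalence and stands immediately before that table, while the comparison with children comes afterwards as an additional claim. The less comfortable limits rest on the boys' figure, which is not a natural comparator for a mixed-sex sample, or on an assumed ICC.

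**Conclusion.** The concern does not hold as a reason to change the plan. The stated 740 and the power above 99% both reproduce at the pilot prevalences. The assurance about a lower prevalence is loose wording for precision, where it is correct. Read as power, it fails against 4.8% only if the true prevalence is about 44% below the pilot (36% with an assumed design effect of 1.98), and nothing in the documents shows an over-estimation of that size. The case definition for the comparison with children is missing detail that the analysts would supply by setting the ICSD-based adolescent figure beside the ICSD-II childhood figure. The sample size and the primary prevalence estimate are untouched.

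This rests on a two-sided 0.05 test, the 4.8% midpoint, a child figure that is fixed or well estimated, and the reading that comparisons are made within a definition.

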The sample selection will be based on a stratified (by districts) and clustered (subjects within randomly selected schools) randomised sampling frame. We stratify all secondary schools registered under the Education Bureau according to the four geographic regions in Hong Kong (i.e. Hong Kong Island, Kowloon, New Territories East and New Territories West). The student numbers in all secondary schools are available in the Bureau's website. Ten students in each school year grade will be randomly selected from the chosen schools. There are on average 50 children to be recruited per schools therefore we will need to randomly select 15 secondary schools from the whole of Hong Kong. In order to avoid sampling bias towards the region that has less population, the final number of schools to be recruited from each of the four geographical regions would be in proportion to the adolescent population that reside in that region. According to the 2016 population by-census statistics (available from the website of Census & Statistics Department, HKSAR), the proportions of adolescents residing in Hong Kong Island, Kowloon, New Territories East and New Territories West were 16.1%, 30.7%, 25.3% and 27.9% respectively. Thus, this study will recruit proportionally 2, 5, 4 and 4 secondary schools from the 4 regions. This sampling method ensures that our subjects are representative of the local school population. Lastly, this study will recruit and survey the subjects from the four regions in parallel throughout the study period in order to minimise the possible influences of different seasons on study outcomes.

Outcome Measures

- (a) Primary outcome: prevalence of obstructive sleep apnoea as defined by obstructive apnoea hypopnoea index.
- (b) Secondary outcomes: correlation between severity of OSA with clinical, laboratory parameters and cognitive function as measured by Conners' Continuous Performance Test (CPT).

Collection of Data

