Blood sample will be taken from the subjects for fasting (at least 8 hours) glucose level, lipid profile, high sensitivity C-reactive protein (hs-CRP), appetite-regulating hormones and pro-inflammatory cytokines determination. Plasma and serum samples will be stored at -80°C until measurement. Plasma glucose is measured by hexokinase method (Cobas C8000 Clinical Chemistry Analyser, Roche Diagnostics Corp, Indianapolis, IN). The inter-assay coefficient of variation is 3% or less at all concentrations up to 41.6 mmol/L. The lipid profile includes total cholesterol (TC), triglyceride (TG), high-density lipoprotein cholesterol (HDL-C), and low-density lipoprotein cholesterol (LDL-C) concentrations, which are measured by appropriate enzymatic assays (Cobas C8000 Clinical Chemistry Analyser, Roche Diagnostics Corp, Indianapolis, IN, USA) with inter-assay coefficients of variation of $\leq 3\%$. Serum hs-CRP will be measured by chemiluminescence immunoassay using the IMMULITE Analyzer (Diagnostic Products Corporation, Los Angeles, CA). Our reference range for hs-CRP is <11.0 mg/L and the sensitivity and inter-assay coefficients of variation are 0.1 mg/L, 6.6% at 1.7 mg/L, 6.5% at 4.8 mg/L and 5.7% at 7.1 mg/L. Ghrelin, leptin, adiponectin and proinflammatory cytokines TNF- α and IL-6 will also be measured using Enzyme-Linked Immunosorbent Assay.

Statistical Analysis

The prevalence of OSA of each geographic region will be calculated individually. The overall prevalence will be calculated using the following formula:

$$\text{Overall prevalence} = \frac{\sum_{i=1}^e N_i \times P_i}{N}$$

where e is the number of strata, N_i is the number of eligible individuals from the population that form part of strata i , P_i is the prevalence of strata i , and N is the number of eligible individuals in the population.

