The resultant prevalence will be compared to published prevalence of OSA in children. Logistic regression analysis will be used to identify possible risk factors of OSA in adolescents. Potential factors associated with a higher risk of OSA may include male sex, body weight, waist circumference, neck circumference, tonsil size, modified Mallampati score and chronotype. All these factors will be first assessed in univariate analysis. Those found to be significantly associated with OSA in univariate analysis will be assessed in multivariate model. The association between OSA and cardiovascular, metabolic and cognitive outcomes will be investigated. Comparisons will be made between subjects with and without OSA. Linear regression analysis will be conducted to assess the association between these outcomes and OAH. Multiple linear regression analysis will be performed to see if OAH is independently associated with these outcome measures while adjusting for possible confounders such as body mass index. The significant level will be set as $p < 0.05$. All analyses will be performed using SPSS version 20.0.

Feasibility and Timetable of Project

The proposed study will require a total of 30 months (130 weeks) to complete. We will be able to assess 8 subjects per week. For a sample size of 740, we will need 93 weeks for data collection. The first 12 weeks will be used for document preparation and school recruitment. The last 15 weeks will be used for data cleaning and analysis. The remaining 10 weeks should be allowed for clashes with schooling, missed appointments and public holidays.

Education plan

The principal investigator and the collaborator are all experienced teachers and supervisors. This project can further strengthen the educational activities and exchanges of the respective departments. It will also provide a good opportunity to train undergraduate and postgraduate students, especially for someone who is interested in the field of sleep medicine. The student will be provided with the required theoretical and practical training, and will work under close supervision of the principal investigator and related research personnel. This will allow the student to learn the knowledge and skills as a scientist, an ideal opportunity to advance himself / herself.

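### The 740 sample size and its stated precisions assume simple random sampling, but the design samples about 50 students in each of 15 schools, and no variance method is given for the primary prevalence interval

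*Combined protocol and SAP*

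**What the plan says.** The primary outcome is the prevalence of OSA, defined by the obstructive apnoea hypopnoea index (OAHI). Under Pilot Data and Sample Size Estimation, Table 1 lists minimum sample sizes by precision for three definitions. The text concludes that "our research team is capable of recruiting 740 adolescents to detect a prevalence of 14.0% with a precision of 2.5" percentage points for OAHI≥5/h (95% CI 11.5–16.5%). It adds that 740 gives better than 4 points for OAHI≥1/h and better than 2.5 points for the ICSD criteria. The pilot prevalences come from a follow-up subgroup with higher baseline severity, and the protocol says "therefore the calculated prevalence is likely an over-estimation".

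The Sampling Frame section describes a "stratified (by districts) and clustered (subjects within randomly selected schools) randomised sampling frame". On size it says: "There are on average 50 children to be recruited per schools therefore we will need to randomly select 15 secondary schools". On allocation: "this study will recruit proportionally 2, 5, 4 and 4 secondary schools from the 4 regions".

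Under Statistical Analysis, "The overall prevalence will be calculated using the following formula", a region-weighted mean of the stratum prevalences. The section then says "The resultant prevalence will be compared to published prevalence of OSA in children", followed by logistic and linear regressions, p<0.05 and SPSS 20.0. It gives no standard error, interval method or survey procedure, and does not mention school.

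**The concern.** Students in one school share catchment, social background and timetable, so their outcomes may be correlated. With about 50 students per school, even a small correlation inflates the variance of the prevalence noticeably. The precision claims make no allowance for this, although the next section of the same document sets out the clustered design.

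Two things are at stake:

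- **The planning claim.** In a prevalence study the interval width is the main planning claim, and the claim for OAHI≥5/h has no slack.
- **The reported interval.** Because no variance method is named, a standard routine that treats the 740 students as independent could be used. The primary interval, and the comparison with childhood prevalence, would then look more certain than they are.

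The regressions are probably less affected, because the listed predictors are measured on individuals.

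**Working it through.** **Inputs from the protocol**
- Pilot prevalences (Table 1): 34/243, 120/243 and 31/243.
- Total sample: 740.
- Design (Sampling Frame): about 50 students per school; 15 schools, split 2, 5, 4 and 4; region shares 16.1%, 30.7%, 25.3% and 27.9%.

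**Assumed input**
- ICC of 0.005, 0.01 and 0.02, applied to all three definitions. The documents give no value.

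**1. Reproduce the plan's figures.** With n = 1.96²·p(1−p)/d²:
- OAHI≥5/h, d = 0.025: 739.65 (stated 740)
- ICSD, d = 0.025: 684.07 (stated 684)
- OAHI≥1/h, d = 0.04: 600.14 (stated 600)

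All 21 cells of Table 1 reproduce this way. At n = 740 the half-widths are 2.50, 3.60 and 2.40 points for OAHI≥5/h, OAHI≥1/h and ICSD, which match the stated precisions. The plan therefore uses a design effect of 1.

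**2. Break-even ICC.** With 1.96, a claim fails once the design effect 1 + 49·ICC exceeds 740/n, so ICC = (740/n − 1)/49:
- OAHI≥5/h: (740/739.65 − 1)/49 ≈ 0
- ICSD: (740/684.07 − 1)/49 = 0.0017
- OAHI≥1/h: (740/600.14 − 1)/49 = 0.0048

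**3. Half-widths under clustering.** Half-width = q·√(p(1−p)·deff/740). The multiplier q is 1.960, or 2.201 for t on 15 − 4 = 11 degrees of freedom. Results are in percentage points, as 1.96 / t:

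| ICC | Design effect | Effective n | OAHI≥5/h | OAHI≥1/h | ICSD |
|---|---|---|---|---|---|
| 0 | 1.00 | 740 | 2.50 / 2.81 | 3.60 / 4.05 | 2.40 / 2.70 |
| 0.005 | 1.245 | 594 | 2.79 / 3.13 | 4.02 / 4.51 | 2.68 / 3.01 |
| 0.01 | 1.49 | 497 | 3.05 / 3.43 | 4.40 / 4.94 | 2.93 / 3.30 |
| 0.02 | 1.98 | 374 | 3.52 / 3.95 | 5.07 / 5.69 | 3.38 / 3.80 |

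The region shares differ slightly from 2/5/4/4 of 15 schools. The weighting multiplies the variance by Σ w²/(share of schools) = 1.009, so the OAHI≥5/h half-width at ICC 0 becomes 2.51.

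**4. If true prevalence is below 14%.** Solving q·√(p(1−p)·deff/740) = 0.025 gives the prevalence below which ±2.5 points still holds. At ICC 0.005, 0.01 and 0.02 it is about 10.8%, 8.9% and 6.5% with 1.96, or 8.4%, 6.9% and 5.1% with t.

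**5. Coverage, by simulation.** The set-up was 40,000 replicates, 15 schools of 49 or 50 students (740 in all) allocated 2, 5, 4 and 4, beta-binomial school prevalences with mean 34/243, and the protocol's region-weighted estimator. No region or grade differences were simulated, so any gain from stratification is left out. Coverage of a nominal 95% interval at ICC 0.005, 0.01 and 0.02:
- Ignoring school: 91.8%, 88.7%, 83.3%
- Design-based variance with t on 11 df: 94–95% throughout
- Same variance with 1.96: about 92%

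**The case against.** - **The size of the loss rests on an ICC the documents do not give.** This stands. At ICC 0.001 or 0.002 the OAHI≥5/h half-width with 1.96 is only 2.56 or 2.62 points, close to a rounding miss. One ICC is also applied to three definitions whose clustering could differ.
- **Part of the loss comes from the t multiplier, not the clustering.** Also true. At ICC 0 the t multiplier alone gives 2.81, 4.05 and 2.70 points, so all three claims fail. For OAHI≥5/h at ICC 0.01, the design effect adds 3.05 − 2.50 = 0.55 points and t adds a further 3.43 − 3.05 = 0.38. But needing t on 11 degrees of freedom is itself a consequence of having only 15 sampled schools.
- **The plan never says it will use a naive interval.** Correct: the undercoverage is conditional. The fault is that the method is left open.
- **14% is likely too high, 740 is set by budget, and the hypothesis test is safe.** The protocol says the first two. A lower prevalence narrows the absolute interval, but does not restore coverage if the variance ignores school. For OAHI≥1/h, near 50%, a moderate fall in prevalence barely changes the width. On power, taking fixed comparators of 3–5.8% from the childhood figures in the protocol as an assumption, power stays at or above 99.6% up to ICC 0.02. The power statement is not challenged.

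These points limit the size of the effect. None of them reconciles the stated precisions with the stated design.

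**Conclusion.** The concern holds and should be corrected before analysis. The stated precisions belong to a simple random sample of 740, which is not what the protocol plans. The OAHI≥5/h claim at 14.0% fails for any positive ICC. The ICSD claim fails above about 0.0017 and the OAHI≥1/h claim above about 0.0048; the latter is marginal at 0.005 (4.02 against under 4). Over assumed ICCs of 0.005 to 0.02, realistic half-widths with t on 11 df are about 3.1–3.9, 4.5–5.7 and 3.0–3.8 points for OAHI≥5/h, OAHI≥1/h and ICSD.

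These sizes depend on the assumed ICC, equal school sizes, the pilot prevalences and no gain from stratification. The mismatch between formula and design, and the absence of a variance method, depend on none of these.

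**What to change.** **Sample size section.** Keep 740 and replace the precision sentences. For example: *Assuming a within-school ICC of 0.005 to 0.02 and t on 11 df, 740 students in 15 schools give a 95% CI half-width of about 3.1 to 3.9 percentage points for OAHI≥5/h at 14.0%, 4.5 to 5.7 for OAHI≥1/h at 49.4%, and 3.0 to 3.8 for the ICSD criteria at 12.8%. Absolute half-widths for OAHI≥5/h and ICSD are smaller if prevalence is lower.*

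**Statistical Analysis section.** State that the prevalence interval and the comparison with childhood prevalence use a design-based variance, with region as stratum, school as cluster and t on 11 df. Say what happens if a region is left with one school: Hong Kong Island has only two, and losing one leaves no within-stratum variance estimate. Report the observed design effect.

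**Secondary.** Fit the regressions with a method that accounts for school and suits 15 clusters. The protocol notes "We have previously established a school-based cohort in 2003-2005". If school was recorded there, it could inform the ICC, with caution because those children were younger and the follow-up subgroup was more severe at baseline.

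**Cost.** Wording only, with no extra students or visits. School must be kept in the dataset, and the stated precision becomes less favourable.
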